## 17.4. WHO Classification of Acute Myeloid Leukemia

### Acute myeloid leukemia with recurrent genetic abnormalities

- Acute myeloid leukemia with t(8;21)(q22;q22); (RUNX1-RUNX1T1)
- Acute myeloid leukemia with inv(16)(p13.1q22) or t(16;16)(p13.1;q22); (CBFB-MYH11)
- Acute promyelocytic leukemia with t(15;17)(q22;q12); (PML-RARA)
- Acute myeloid leukemia with t(9;11)(p22;q23); MLLT3-MLL
- Acute myeloid leukemia with t(6;9)(p23q34); DEK-NUP214
- Acute myeloid leukemia with inv(3)(q21q26.2) or t(3;3)(q26.2); RPN1-EVI1
- Acute myeloid leukemia (megakaryoblastic) with t(1;22)(p13;q13); RBM15-MKL1
- Acute myeloid leukemia with gene mutations

### Acute myeloid leukemia with myelodysplasia-related changes

#### Therapy-related myeloid neoplasma

### Acute myeloid leukemia, not otherwise categorized

- Acute myeloid leukemia with minimal differentiation
- Acute myeloid leukemia without maturation
- Acute myeloid leukemia with maturation
- Acute myelomonocytic leukemia
- Acute monoblastic and monocytic leukemia
- Acute erythroid leukemia (erythroid/myeloid and pure erythroleukemia)
- Acute megakaryoblastic leukemia
- Acute basophilic leukemia
- Acute panmyelosis with myelofibrosis

Source: 

### 17.5. Eastern Cooperative Oncology Group (ECOG) Performance Status

---

Grade	ECOG
0	Fully active, able to carry on all predisease performance without restriction
1	Restricted in physically strenuous activity but ambulatory and able to carry out work of a light or sedentary nature, eg, light house work, office work
2	Ambulatory and capable of all self care but unable to carry out any work activities. Up and about more than 50% of waking hours
3	Capable of only limited self care, confined to bed or chair more than 50% of waking hours
4	Completely disabled. Cannot carry on any self care. Totally confined to bed or chair
5	Dead

---

Source:

[REDACTED]

### 17.6. Risk Status Based on Cytogenetics

Risk Status	Cytogenetics
Better-risk	inv(16)  t(16;16)  t(8;21)  t(15;17)
Intermediate-risk	Normal cytogenetics +8 t(9;11) Other non-defined
Poor-risk	Complex ( $\geq 3$ abnormalities) -5 5q- -7 7q- 11q23 - non t(9;11) inv(3) t(3;3) t(6;9) t(9;22) 

1 Other abnormalities in addition to these finding do not alter risk status

2 Philadelphia+ AML t(9;22) consider managing as myeloid blast crisis in CML. These subjects are excluded from study entry.

Source:

### 17.7. International Working Group AML Response Criteria

Hematologic Response According to IWG Criteria for AML	
Category	Definition
Morphologic Complete Remission (CR)	The following conditions should be met: 
 
• ANC > 1,000/<math>\mu</math>L;
 
• Platelet count <math>\geq</math> 100,000/<math>\mu</math>L;
 
• The bone marrow should contain less than 5% blast cells;
 
• Auer rods should not be detectable;
 
• No evidence of extramedullary disease;
 
• Independent of transfusions.
 

Morphologic Complete Remission with Incomplete Blood Count Recovery (CRi)	Defined as a morphologic complete remission but the ANC count may be < 1,000/ $\mu$ L or the platelet count may be < 100,000/ $\mu$ L.
Cytogenetic Complete Remission (CRc)	Defined as morphologic complete remission with a reversion to a normal karyotype.
Relapse Free Survival	Defined for patients who achieve CR/CRi, and is measured from the date of attaining leukemia free state until the date of AML relapse or death from any cause, whichever occurs first.
Disease Relapse	Relapse after CR/CRi is defined as reappearance of leukemic blasts in the peripheral blood or $\geq$ 5% blasts in the bone marrow not attributable to any other cause (eg, bone marrow regeneration after consolidation therapy). In the setting of recent treatment, if there are no circulating blasts and the bone marrow contains 5% to 20% blasts, a repeat bone marrow performed at least a week later is necessary to distinguish relapse from regeneration.

Source:

**17.8. Grades for select laboratory analytes based on CTCAE v4.0**

The definitions in Tables 1 and 2 are based on the criteria specified in the CTCAE v4.0. In cases where the criteria for a grade are based on signs and symptoms in conjunction with lab results, the grade is based only on observed lab values. In cases where the same value of a lab result is used in defining more than one grade, the definition for the highest (worst) grade is implemented.

**Table 6. Definitions for select Hematology analytes**

Analyte	Grade 0	Grade 1	Grade 2	Grade 3	Grade 4
Hgb (anemia)	$\geq$ LLN	100 g/L - < LLN	80 g/L - < 100 g/L	65 g/L - < 80 g/L	< 65 g/L
Platelets (decreased)	$\geq$ LLN	75.0 x 10  /L - < LLN	50.0 - < 75.0 x 10  /L	25.0 - < 50.0 x 10  /L	< 25.0 x 10  /L
ANC (decreased)	$\geq$ LLN	1.5 x 10  /L - < LLN	1.0 - < 1.5 x 10  /L	0.5 - < 1.0 x 10  /L	< 0.5 x 10  /L
WBC (decreased)	$\geq$ LLN	3.0 x 10  /L - < LLN	2.0 - < 3.0 x 10  /L	1.0 - < 2.0 x 10  /L	< 1.0 x 10  /L

All values given in SI units. ND = Not defined in terms of laboratory values.

**Table 7. Definitions for select Chemistry analytes**

Analyte	Grade 0	Grade 1	Grade 2	Grade 3	Grade 4
Hypoalbuminemia (decreased albumin)	$\geq$ LLN	30 g/L - < LLN	20 g/L - < 30 g/L	< 20 g/L	ND
Alkaline Phosphatase (increased)	$\leq$ ULN	> ULN - 2.5 x ULN	>2.5 – 5.0 x ULN	>5.0 - 20.0 x ULN	> 20.0 x ULN
Bilirubin, Total (increased)	$\leq$ ULN	> ULN - 1.5 x ULN	> 1.5 - 3.0 x ULN	>3.0 - 10.0 x ULN	>10.0 x ULN
SGPT* (AST) (increased)	$\leq$ ULN	> ULN - 3.0 x ULN	>3.0 - 5.0 x ULN	>5.0 - 20.0 x ULN	> 20.0 x ULN
SGOT *(ALT) (increased)	$\leq$ ULN	> ULN - 3.0 x ULN	>3.0 - 5.0 x ULN	>5.0 - 20.0 x ULN	> 20.0 x ULN
Creatinine (increased)	$\leq$ ULN	> ULN - 1.5 x ULN	> 1.5 - 3.0 x ULN	>3.0 - 6.0 x ULN	> 6.0 x ULN
Hypercalcemia (increased calcium)	$\leq$ ULN	> ULN - 2.9 mmol/L	> 2.9 - 3.1 mmol/L	> 3.1 - 3.4 mmol/L	> 3.4 mmol/L
Hypocalcemia (decreased calcium)	$\geq$ LLN	2.0 mmol/L - < LLN	1.75 - < 2.0 mmol/L	1.5 - < 1.75 mmol/L	< 1.5 mmol/L
Hyperglycemia (increased glucose)	$\leq$ ULN	> ULN - 8.9 mmol/L	> 8.9 - 13.9 mmol/L	> 13.9 - 27.8 mmol/L	> 27.8 mmol/L
Hypoglycemia (decreased glucose)	$\geq$ LLN	3.0 mmol/L - < LLN	2.2 - < 3.0 mmol/L	1.7 - < 2.2 mmol/L	< 1.7 mmol/L

Analyte	Grade 0	Grade 1	Grade 2	Grade 3	Grade 4
Hypernatremia (increased sodium)	$\leq$ ULN	$>$ ULN - 150 mmol/L	$>$ 150 - 155 mmol/L	$>$ 155 - 160 mmol/L	$>$ 160 mmol/L
Hyponatremia (decreased sodium)	$\geq$ LLN	130 mmol/L - $<$ LLN	ND	120 - $<$ 130 mmol/L	$<$ 120 mmol/L
Hyperkalemia (increased potassium)	$\leq$ ULN	$>$ ULN - 5.5 mmol/L	$>$ 5.5 - 6.0 mmol/L	$>$ 6.0 - 7.0 mmol/L	$>$ 7.0 mmol/L
Hypokalemia (decreased potassium)	$\geq$ LLN	ND	3.0 mmol/L - $<$ LLN	2.5 - $<$ 3.0 mmol/L	$<$ 2.5 mmol/L
Hypophosphatemia (decreased phosphates)	$\geq$ LLN	0.8 mmol/L - $<$ LLN	0.6 - $<$ 0.8 mmol/L	0.3 - $<$ 0.6 mmol/L	$<$ 0.3 mmol/L
Hyperuricemia (increased uric acid)	$\leq$ ULN		ND	$>$ ULN - 0.59 mmol/L	$>$ 0.59 mmol/L

All values given in SI units. ND = Not defined in terms of laboratory values.

\*SGPT and SGOT grades based strictly on laboratory values without consideration for presence or absence of symptoms.

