11. Includes a complete blood count (RBC count, hemoglobin, hematocrit, mean corpuscular volume [MCV], mean corpuscular hemoglobin [MCH], mean corpuscular hemoglobin concentration [MCHC], WBC count with differential, ANC, and platelet count). Any or all laboratory assessments may be repeated more frequently if clinically indicated. The samples will be collected prior to study treatment dosing and will be analyzed by the central laboratory. In the event that hematology laboratory results are needed to acutely manage the subject, local laboratory tests may be used. In addition to the local laboratory sample, a second sample should always be sent to the central laboratory.
12. Serum ferritin levels will be collected at screening, on Day 1 of Cycle 1, on Day 1 of every 3 cycles thereafter (ie, Day 1 of Cycles 4, 7, 10, 13, etc.) and at the Treatment Discontinuation visit.
13. Whenever a hematology sample is collected for a complete blood count, an unstained peripheral blood smear should be prepared and sent to the central laboratory. This unstained peripheral blood smear will be used to assess a manual blood count differential.
14. Includes serum chemistry labs (sodium, potassium, chloride, bicarbonate, calcium, phosphorus, BUN, creatinine, glucose, albumin, total protein, alkaline phosphatase, direct/indirect total bilirubin, aspartate aminotransferase [AST], alanine aminotransferase [ALT], lactate dehydrogenase [LDH], and uric acid). The samples will be collected prior to study treatment dosing and will be analyzed by the central laboratory. Any or all laboratory assessments may be repeated more frequently if clinically indicated. In the event that chemistry laboratory results are needed to acutely manage the subject, local laboratory tests may be used. In addition to the local laboratory sample, a second sample should be sent to the central laboratory.
15. A medically supervised serum pregnancy test with sensitivity of at least 25mIU/mL is to be obtained in female subjects of childbearing potential (FCBP) at Screening (within 72 hours prior to starting study therapy). A serum or urine pregnancy test (per Investigator’s discretion) is to be done prior to Day 1 of every subsequent cycle (within 72 hours), and at the End of the Treatment visit. The subject may not receive investigational product until the Investigator has verified that the result of the pregnancy test is negative.

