### **12.4. Clinical Laboratory Evaluations**

The laboratory assessments prior to and including the date of first dose of study medication will be considered pre-treatment. The baseline value is defined as the last (most recent) non-missing value during the pre-treatment period. The laboratory data collected after date of discontinuation from the treatment period (date of last dose of IP + 28 days or end of treatment visit, whichever is longer) will be considered post-treatment.

Clinical laboratory values from the central laboratories will be graded according to CTCAE version 4.0 for selected tests (see [Appendix 17.8](#) for list of tests). Summary statistics (N, Mean, SDev, Median, Minimum, and Maximum) of observed and change from baseline values will be presented for each lab test at each scheduled visit. Frequency distributions for shift from baseline to worst CTCAE grade observed across all cycles and within each cycle will be displayed by treatment arm for CTCAE graded tests. Clinical laboratory values with a CTCAE grade of 3 or 4, observed during treatment will be summarized (counts and percentages) by cycle for CTCAE graded tests. Listings of clinical laboratory data with abnormal flags will be provided by subject and test.

Nadirs (minimum values) of selected hematology parameters (Hgb, platelets, ANC, WBC and RBC) across all cycles and within each cycle will be summarized by cycle onset day using frequency distributions (counts and percent). Additionally, the average onset day of nadir will be summarized across all cycles using descriptive statistics. The earliest cycle day on which the lowest value was observed will be used as the onset day of the nadir. In addition, descriptive

statistics of the analyte values at nadir and change from baseline to nadir value will be provided for each selected hematology test.

Graphical display of select laboratory parameters over the course of the study will be provided.

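### SAP Table 7 grades every uric acid value above the upper limit of normal as 3 or 4, so minor elevations enter the uric acid rows of the Grade 3/4 and shift tables

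*SAP*

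**What the plan says.** SAP 17.8 lays down two rules for laboratory grading. Where the toxicity criteria combine symptoms with a result, "the grade is based only on observed lab values". Where one result would fit more than one grade, "the definition for the highest (worst) grade is implemented".

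Table 7 then sets out the row "Hyperuricemia (increased uric acid") as follows:

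| Grade | Uric acid |
|---|---|
| 0 | at or below ULN |
| 1 | blank |
| 2 | ND |
| 3 | above ULN to 0.59 mmol/L |
| 4 | above 0.59 mmol/L |

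The table footnote reads "ND = Not defined in terms of laboratory values".

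Uric acid is part of the routine central-laboratory chemistry panel. The list in the Protocol's Table of Events ends with "alanine aminotransferase [ALT], lactate dehydrogenase [LDH], and uric acid", and the panel is drawn on Day 1 of each cycle. SAP 12.4 says how the grades are used: "Clinical laboratory values with a CTCAE grade of 3 or 4, observed during treatment will be summarized (counts and percentages) by cycle". It also calls for shift tables from baseline to worst grade, across all cycles and within each cycle. Protocol 10.7 describes the corresponding summary as one of clinically significant abnormalities meeting Grade 3 or 4. SAP 12.4 has no such qualifier, and SAP section 15, which lists changes from the protocol, does not mention the difference.

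**The concern.** A reader of a Grade 3/4 laboratory table takes Grade 3 to mean a marked abnormality. For uric acid it will mean anything above normal. A value barely over the limit and one just under 0.59 mmol/L fall in the same Grade 3 cell, and neither mild category can ever be filled.

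The shift table loses information in two ways. A trivial move across ULN shows as a jump from Grade 0 to Grade 3. A subject slightly above ULN at baseline starts at Grade 3 and shows no shift until the value passes 0.59 mmol/L. At stake is how far the uric acid rows of two safety outputs can be read and compared with the other rows.

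**Working it through.** The SAP states no figure to reproduce, so the check is of the grading logic, followed by an illustration of size.

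**Step 1. Grades reachable.** Take a value v with ULN < v ≤ 0.59 mmol/L. It fails Grade 0, meets the printed Grade 3 range, and fails Grade 4. Grade 2 has no laboratory definition. The assigned grade is 3. If v > 0.59 mmol/L, the grade is 4. Nothing above ULN can be Grade 1 or 2.

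**Step 2. Does the blank cell matter?** The blank may be the SAP's own or may have been lost when the file was converted to text. If it really is blank, Grade 3 is the only grade that fits. If it held the same range as Grade 3, or any range overlapping it, the worst-grade rule would still return 3. The documents do not give the ULN, so this was run with assumed values of 0.36, 0.42 and 0.48 mmol/L. In each case a value 0.1% above ULN (0.3604, 0.4204 and 0.4805 mmol/L) was Grade 3, and the only grades reached above ULN were 3 and 4, with the Grade 1 cell blank or filled.

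**Step 3. Is this row unusual?** Table 6 has 4 graded rows and Table 7 has 16, making 20. In the other 19, at least one numeric Grade 1 or Grade 2 band lies between normal and Grade 3:

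| Analyte | Grade 3 starts |
|---|---|
| Alkaline phosphatase, AST, ALT | above 5 × ULN |
| Total bilirubin, creatinine | above 3 × ULN |
| Hyponatremia (Grade 2 ND) | below 130 mmol/L, after a Grade 1 band |
| Hypokalemia (Grade 1 ND) | below 3.0 mmol/L, after a Grade 2 band |
| Uric acid | immediately above ULN |

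**Step 4. Possible size (illustration only).** Let p be the share of samples above ULN and k the number of samples per subject. Both are assumptions. The share of subjects with at least one Grade 3/4 uric acid value is p if a subject's samples are fully correlated, and 1 − (1 − p)^k if they are independent. With k = 6 and the planned 230 subjects per arm:

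| p | Fully correlated | Independent, 1 − (1 − p)^6 |
|---|---|---|
| 2.5% | 2.5% (about 6 subjects) | 1 − 0.975^6 = 14.1% (32) |
| 5% | 5% (about 12) | 1 − 0.95^6 = 26.5% (61) |
| 10% | 10% (23) | 1 − 0.90^6 = 46.9% (108) |
| 20% | 20% (46) | 1 − 0.80^6 = 73.8% (170) |

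With k = 12 and p = 2.5% the range is 2.5% to 26.2%. The spread comes from the assumptions on p, k and correlation, and none of these rows estimates what this trial would show.

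**The case against.** The strongest reply is that this is a stated convention. SAP 17.8 announces both rules in advance, they apply identically in the two arms, and a table built on them follows its own definition. That stands: the output would be misleading, not erroneous, and there is no contradiction within Table 7. Announcing the rule does not make this row's Grade 3 comparable with any other.

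A reader might infer more, and three such inferences fail.

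- **That the Grade 3/4 laboratory tables as a whole fill with trivial findings.** SAP 12.4 works from CTCAE-graded tests and specifies no pooled line for any Grade 3/4 abnormality. One row of 20 is affected.
- **That the tumour lysis assessment is weakened.** SAP 12.2.1 builds that category from adverse event terms, not laboratory grades. Severity is assigned by the investigator (SAP 12.1), and a laboratory result becomes an adverse event only on the clinical criteria in Protocol 6.6.6 and 11.3.
- **That a real rise in uric acid would be hidden.** SAP 12.4 also summarises observed values and change from baseline at each scheduled visit and provides flagged listings, and Grade 4 remains its own shift category. Resolution is lost in the combined Grade 3/4 count and in shifts within the Grade 3 band.

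Protocol 10.7 can be read as a filter or merely as a description. On either reading, a value just over ULN is not an obvious case of a clinically significant abnormality.

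**Conclusion.** The point holds for the uric acid row alone. As written, SAP 17.8 and Table 7 make every value above ULN Grade 3 or 4, and SAP 12.4 passes that into the by-cycle counts and shift tables in both arms. This follows from the printed Grade 3 range whatever the Grade 1 cell was meant to contain; it presupposes only a ULN below 0.59 mmol/L, as the printed range itself does.

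The number of subjects affected cannot be derived from the documents. The percentages in the working rest on assumed frequencies, sample counts and correlation. The other 19 graded rows, adverse event severity, the adverse events of special interest and all efficacy analyses are unaffected. This is a minor, worthwhile correction.

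**What to change.** Change the uric acid row only, in one of two ways.

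1. Move the band from above ULN to 0.59 mmol/L into the lowest grade for laboratory-only grading, take it out of Grade 3, and state in 17.8 that uric acid is an exception to the worst-grade rule. Values above 0.59 mmol/L stay Grade 4, and only these count towards Grade 3/4. The cell and the sentence must change together, since either alone leaves the row ambiguous.
2. Report uric acid in two bands, above ULN to 0.59 mmol/L and above 0.59 mmol/L, in place of Grade 3/4. This makes no claim about what the lower band should be called.

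Two remedies should be avoided. A general rule that the symptom-free grade applies would contradict the worst-grade rule beside it, and its effect on other rows (hypokalemia, for one, has Grade 1 undefined) would need checking. Bringing grades from the adverse event page into this table would mix two sources in an output defined as laboratory-only.

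While 17.8 is open, align SAP 12.4 with the wording of Protocol 10.7, or record the difference in SAP section 15, and correct the reference to Tables 1 and 2, since the grading tables are numbered 6 and 7.

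The cost is a table edit, one sentence in the SAP and the matching program change, with no new data. The downside is that a symptomatic elevation up to 0.59 mmol/L would appear as severe only in the adverse event tables.
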